The Benefit of Mindfulness-Based Intervention Using A Wearable Wellness Brain Sensing Device in the Treatment of Post Covid Symptoms

NCT05199233

07 Nov 2024

Mayo Clinic - NCT05199233

General Study Information

Principal Investigator: [name]

Co-principal investigators: [name] MD

Study Title: The Benefit of Mindfulness-Based Intervention Using A Wearable Wellness Brain Sensing

Device (Muse-STM) in the Treatment of Post Covid Symptoms

As of 07 Nov 2024

Research Ouestion and Aims

Hypothesis:

Post acute sequelae of SARS-CoV-2 infection (PASC), also known as "long haul covid" or Post-COVID Syndrome, is a significant cause of morbidity and disability in patients who have had COVID-19 with an estimated 10-30% of patients developing PASC with symptoms lingering for months and even years. These symptoms occur in a typical pattern, often including fatigue with post-exertional malaise, dyspnea, widespread pain, subjective cognitive dysfunction (often referred to as "brain fog"), and orthostatic intolerance and remain persistent. These can manifest in the post-covid patient as difficulty breathing or shortness of breath, tiredness or fatigue, difficulty thinking or concentrating, cough, chest and/or stomach pain, headache, palpitations, joint and/or muscle pain, parasthesias, diarrhea, increased anxiety and stress, as well as sleep problems.

We postulate that using a novel biofeedback-assisted meditation device (Muse-STM) daily can enhance calm state brain activity and parasympathetic nervous system activity in post-covid patients. We hypothesize that greater amount of time the patient uses this tool will directly correlate with improvements in stress, resilience, and overall quality of life.

Aims, purpose, or objectives:

In this study 60 patients diagnosed with Post-Covid Syndrome (PASC) at Mayo Clinic Rochester will be enrolled in this study.

Primary:

- 1. To study the feasibility of using a wearable brain-sensing wellness device (Muse-STM) to potentially reduce stress and anxiety during Post-Covid, which is characterized with increased stress and anxiety.
- 2. To assess the association between usage of the wearable brain-sensing wellness device (Muse-STM), and quality of life (QOL), subjective stress, anxiety, cognition, through self-assessment surveys.

Exploratory:

1. To collect data at month 6 (3 months post end of treatment) on continued use of Muse-STM past the treatment phase, as a proxy for lifestyle changes.

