Wearable for LC PIs: [name]; [name], PhD Mayo Clinic - NCT05199233

The primary outcome will be the adherence to the Muse-STM by summarizing the frequency of use and duration of use each time it was accessed.

The secondary outcomes will include:

o change in quality of life (QOL), stress, anxiety, and cognition, score over time

Background:

According to the CDC, new or ongoing symptoms of long COVID may include difficulty breathing or shortness of breath, tiredness or fatigue, difficulty thinking or concentrating, cough, chest and/or stomach pain, headache, heart palpitations, joint and/or muscle pain, pins and needles, diarrhea, sleep problems; all of which can increase anxiety and stress in the post-covid patient.

Integrative Medicine has introduced many mind-body therapies for addressing mental stress. The top stress relievers recommended by Mayo Clinic include: getting active, eating a healthy diet, avoiding unhealthy habits, meditation, laughing more, connecting with others, asserting yourself, practicing yoga, getting enough sleep, keeping a journal, exploring music and being creative, seeking counseling². Among all of these potential options, meditation is the easiest to incorporate in a current lifestyle yet most difficult to undertake without proper training and guidance at the beginning. Muse-STM is a clinical grade, headband-style wireless EEG system designed to interact with a mobile device (a smartphone or tablet) (https://choosemuse.com). In combination with the Muse-STM APP running on iOS or Android smartphones, Muse-STM converts EEG signals measured over the frontal and temporal cerebral cortices into measures of brain state. At the same time Muse-STM can also guide the user through the meditation steps. Calibrated to an individual user, Muse-STM distinguishes between active and calm brain states to provide real-time performance feedback, and helps users realize the benefits of mindfulness practice in an engaging and accessible manner. Muse-STM also has a PPG sensor that tracks heartrate during meditation sessions as well. This has been tested in a prior study by some of the current study team (SP and ITC), with patients undergoing breast cancer surgery³ and is currently being test in patients with fibromyalgia who concurrently experience pain (ITC and RG) and in healthcare providers who are under stress (ITC).

Study Design and Methods

Methods:

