be able to see their own data at the end of each session, and data from the previous session stored in the "me" tab in the app. Subject to the study organizers ensuring that the subjects have signed the appropriate consents, study organizers will have access to each subject's data to monitor compliance, performance and outcomes, but will not get access to Journal entry information (if subject chooses to write a Journal entry). These data that the study organizers will have access can include the study-specific identification number, gender, and age of the subject, the session type, the time and duration of each session, EEG data, heart rate (PPG) data, and the performance per session. Interaxon's privacy policy, which can be found at www.choosemuse.com/privacy will apply to Interaxon's use of the subjects' data. In order to maximize protection of the individual's privacy, the study organizers will ensure that the subjects are assigned anonymized email address and names for use in the Muse -STM application and when contacting the Muse-STM customer support. To ensure that no health data is shared with Interaxon, the study organizers have agreed to ensure that no health data will be shared. At the end of the study, the data collected in Google iCloud Server associated with study email addresses will be deleted.

- O The Muse-STM steps include: 1) Open the Muse-STM App on subject device. 2) select meditation type 3) if meditating with the headband, turn on the Muse-STM headband. It will pair via bluetooth to the app 4) put on headband (if doing a meditation with headband) 5) meditate 6) add any journal or mood entry if desired 7) review results
- O Cleaning the Muse-STM: Each patient will be given a brand new, out-of-the-box Muse-STM Headband system. If cleaning must occur, the entire Muse-STM including the headset can be wiped down with a standard disinfectant wipe. The band can also be hand-washed gently with soap and water. The module on the band is not waterproof but can be wiped with disinfectant.

Tracking Vitals:

Fitbit Tracker:

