Demographic characteristics are described using mean and standard deviations or frequencies and percentages based on the type of variable. For the primary aim of assessing feasibility, descriptive statistics and graphical displays will be presented for data obtained on frequency and duration of use over the 12 weeks of treatment. A linear mixed model with repeated measures for each time point that stress and sleep were taken will be utilized to estimate the association between the number of sessions spent using the Muse-STM with the stress and sleep level outcome. As secondary outcomes, the results of the LASA, resilience, coping, and cognitive testing will be analyzed using similar mixed models. In all cases, results will be summarized using point estimates and corresponding 95% confidence intervals. Given the number of outcomes assessed, all analyses will be considered exploratory.

Endpoints:

Primary Hypothesis:

a) Post Covid patients enrolled in this study will find the Muse-STM Headband system easy to use and will use it per protocol.

Secondary Hypotheses:

- a) Stress score will be lower and sleep score will be improved when compared to the baseline measures for those who use the Muse-STM system as directed.
- b) As the use of the Muse-STM system increases, QOL, resilience and coping will improve.

References

1. Ninifaggi F. Physician engagement: mindfulness as part of the pandemic solution. Elsevier Connect. https://www.elsevier.com/connect/physician-engagement-mindfulness-as-part-of-the-pandemic-solution. Updated 11 May 2020. Accessed 11 June 2020, 2020.

- 2. Mayo Clinic Staff. Stress Management. Healthy Lifestyle Web site.

 https://www.mayoclinic.org/healthy-lifestyle/stress-management/in-depth/stress-relievers/art-20047257. Updated 12 March 2019. Accessed 01 June 2020.

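### The hypothesis is about time spent using the device, but the planned models use only the number of sessions, so the time-based hypothesis is not tested as written

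*Combined protocol and SAP*

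**What the plan says.** The Hypothesis section, under the research question and aims, states the expected relation in units of time: "greater amount of time the patient uses this tool will directly correlate with improvements in stress, resilience, and overall quality of life".

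The Data Analysis Plan specifies a linear mixed model with repeated measures to estimate "the association between the number of sessions spent using the Muse-STM with the stress and sleep level outcome". For the remaining outcomes it says that "the results of the LASA, resilience, coping, and cognitive testing will be analyzed using similar mixed models". It names no other exposure.

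Duration appears in three places:
- The primary outcome is adherence, obtained by "summarizing the frequency of use and duration of use each time it was accessed".
- The Server Data paragraph lists what the study team can obtain, including "the session type, the time and duration of each session, EEG data, heart rate (PPG) data, and the performance per session".
- For the feasibility aim, the Data Analysis Plan says that descriptive statistics and "graphical displays will be presented for data obtained on frequency and duration of use over the 12 weeks of treatment".

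No planned model contains duration. The plan does not say what counts as a session, and it sets no minimum length or weighting.

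**The concern.** A session count equals time on the device, up to a constant, only if sessions are about equally long. The protocol leaves length open. The Methods section asks for ten minutes or longer, four or more times a week, with no upper limit. The Mind Meditation description recommends daily use with a five-minute floor and allows more. The sleep section lets the participant keep the headband on overnight. As written, a short breathing exercise and an overnight recording could each add one to the count.

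What is at stake is the second primary aim, the association between usage and the self-reported outcomes. The count model answers a related question about frequency, and the question in the hypothesis goes unanswered although the data to answer it are held. The feasibility aim is not affected.

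**Working it through.** The plan gives no power calculation, variance or effect size, so there is no figure of its own to reproduce. The check has a textual part and an illustrative part.

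**1. Exposure named against exposure modelled**
- Hypothesis section: amount of time.
- Stress and sleep model: number of sessions.
- Quality of life, resilience, coping and cognitive testing: similar models, no separate exposure.
- Duration: descriptive statistics and graphs only.

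**2. Range of time at one exposure value**
- Requested minimum (Methods): 4 × 12 = 48 sessions, and 48 × 10 = 480 minutes.
- 48 sessions of 5 minutes: 240 minutes.
- 48 sessions of 20 minutes: 960 minutes.

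The last two differ four-fold in time but get the same value in the model. The 5-minute figure comes from the Mind Meditation description. The 20-minute figure is an illustration.

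**3. How well count stands in for minutes**

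Let N be a person's number of sessions, L their mean session length and T = N × L their total minutes. If N and L are independent,

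corr(N, T) = CV_N / √(CV_N² + CV_L² + CV_N² CV_L²).

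Assume CV_N = 0.6, a minutes-outcome correlation of 0.4, and an outcome that depends on use only through minutes. The count-outcome correlation is then 0.4 × corr(N, T). With n = 60 and a two-sided 5% level, the Fisher-z approximation gives

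power = Φ(atanh(r) × √57 − 1.96).

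For minutes: atanh(0.4) × √57 − 1.96 = 3.20 − 1.96 = 1.24, so power is 89%.

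For count:

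| CV of length | corr(N, T) | r with outcome | Power, Fisher z | Power, simulated |
|---|---|---|---|---|
| 0.1 | 0.98 | 0.393 | 88% | 87% |
| 0.2 | 0.93 | 0.373 | 84% | 83% |
| 0.3 | 0.86 | 0.346 | 78% | 77% |
| 0.5 | 0.72 | 0.287 | 61% | 60% |
| 1.0 | 0.46 | 0.183 | 29% | 30% |

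The simulation used 20,000 runs with gamma-distributed count and length. In it, power with minutes was 88% to 89% at length CVs of 0.1 to 0.3, 87% at 0.5 and 82% at 1.0. Both calculations are for a cross-sectional correlation and do not reproduce the repeated-measures model.

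**4. Precision or bias**

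The regression slope of T on N is cov(N, T)/var(N). With N and L independent this equals the mean session length, so the per-session slope is the per-minute effect times mean length, without bias. A separate simulation used lognormal N and L and a count CV of 0.4 to 0.6. It gave these ratios of the slope to its unbiased value:

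| Correlation of log N and log L | Length CV 0.25 | Length CV 0.5 |
|---|---|---|
| 0 | 1.00 | 1.00 |
| −0.5 (frequent users take shorter sessions) | 0.63 to 0.70 | 0.33 to 0.47 |
| +0.5 (frequent users take longer sessions) | 1.35 to 1.42 | 1.74 to 1.85 |

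A model with count alone cannot show which row applies.

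**The case against.** The strongest case on the other side has five parts.

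- **The hypotheses listed next to the analysis plan name no unit.** The Endpoints section speaks of use as directed and of increasing use, and the second primary aim speaks of usage. Only the Hypothesis section says time. This stands, and it means that restating that one sentence in sessions would also remove the mismatch. It does not make the present text consistent.
- **Duration is not ignored.** A reader might infer that it is dropped altogether. The documents do not support that: it is part of the primary outcome and will be described over the 12 weeks, so readers will see how much it varies. Description still does not relate time to outcome.
- **The power loss follows from assuming that minutes are the dose.** This stands. If count were the true dose, the same formula would show the same loss for minutes. The request for ten minutes or longer could also make lengths cluster, and the loss would then be small.
- **The analyses are declared exploratory and reported with 95% confidence intervals.** Detection at the 5% level is therefore not the plan's decision rule, and the power figures only express lost precision.
- **Raw minutes have a fault of their own.** Overnight wear could dominate them. This stands and shapes the fix.

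A reader might also infer that the count-based association is necessarily weakened, or that a real relation will be missed. The documents do not support either. They give no spread of session lengths, and with length independent of count the slope is not biased.

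**Conclusion.** The mismatch holds on the text: the hypothesis is in time, every planned usage model is in sessions, and the logged duration enters none of them. The time-based hypothesis is therefore not tested as written.

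The consequence is conditional. If session length differs between people, the count is a less precise measure of the time relation. Bias, in either direction, arises only if length and count are correlated. Under the stated assumptions (minutes the true dose, correlation 0.4, n = 60, count CV 0.6) the loss runs from about 1 to 5 points of power at a length CV of 0.1 to 0.2 up to about 60 points at a length CV of 1.0 (89% against roughly 30%). The documents cannot say where in that range the trial lies.

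The point affects how the exploratory usage-outcome association is read. It is worth correcting because the data are already collected and the change is small.

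**What to change.** In the Data Analysis Plan, add cumulative meditation minutes up to each visit, taken from the server log, as the exposure that tests the hypothesis. Report the session-count model alongside it. Use the logged session type to keep sleep and overnight sessions separate, and state what counts as a session. If frequency was the intended exposure, restate the sentence in the Hypothesis section in sessions instead.

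The cost is one derived variable, a rule for go-to-sleep sessions that run into overnight wear, and one extra exploratory model per outcome. No new data collection is needed.

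Separately, the instructions on use differ between the Methods section (four or more sessions a week, ten minutes or longer) and the Intervention section (daily practice, with a five-minute daily floor for one meditation type). These must be reconciled, since they bear on what a session and adequate use mean in the analysis.

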All study participants will receive the Muse S^{TM} Headband system at study entry and will be asked to utilize it at least 4 times per week for a minimum of 10 minutes each time over a period of 3 months (12 weeks). They will be followed for a period of 6 months (3 months of treatment and 3 months post treatment) according to the schedule below.

We arable for LC

Pls: [name]; [name], PhD

Mayo Clinic - NCT05199233

	Consent /screen /baseline	Treatment Phase				Follow up Phase
Visit No.	1	2	3	4	5	6
Visit Type	Face to Face	Phone	Phone/ Email	Phone/ Email	Face to Face/ Phone/ Email	Face to Face/ Phone/ Email
Visit Days	0	2	30	60	90	180
Consent/Screening/						
Enrollment						
Informed Consent	X					
Inclusion/Exclusion	X					
Demographic and History	X					
Form	Λ					
Safety Data						
Depression	X		X	X	X	X
Adverse Events ¹			X	X	X	X
Concomitant Medication ²	X		X	X	X	X
Intervention						
Instructions for Muse-S TM & Fitbit [®] Tracker	X					
Muse-S TM use	X		X	X	X	
Fitbit [®] Tracker		X			X	X
Outcome						
CBS Cognitive Tests	X				X	X
Anxiety	X		X	X	X	X
Cognition Function	X		X	X	X	X
Emotional Distress	X		X	X	X	X
Quality of Life	X		X	X	X	X
Resilience	X		X	X	X	X
Self-Efficacy	X		X	X	X	X
Sleep	X		X	X	X	X
Stress Scale	X		X	X	X	X
Satisfaction Survey						X
End of Study Forms						X

^{1 =} For visit 5 & 6 only serious adverse events will be newly collected; 2 = For visit 5 & 6, only newly added concomitant medications will be collected

Study Visit Windows:

Each visit will have a window from the midpoint of the prior visit to the midpoint of the latter visit.

Data Collection:

Mayo Clinic - NCT05199233

Subjects will have the options of completing study surveys/questionnaires online via email link to REDCap prior to study visit. If not completed by the time the study visit takes place, the coordinator can provide the iPad digital version of the survey/questionnaire to the subject for the in-person visits or can interview the patient via phone for the telephone visits. If a subject misses a visit, the study staff will connect with the subject to collect what study data is appropriate through a simple virtual connection (email redcap surveys or telephone interview of surveys). Data Collection in this study will utilize REDCap⁴. All other data collection will be entered directly into a password protected system.

Assessments:

Safety:

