Please note: Patients must have access to an iOS or Android capable device to take part in this study in order to interact with the Muse-STM Headband system.

Treatment phase:

During the first three months of study, participants will be asked to complete the online study intervention using the Muse-STM headband. Participants will be contacted via telephone and online (REDCap) for study visits at day 2, 30 and 60. At day 90, they will be asked to return to the clinic for an in-person visit (telephone and online will be alternatives).

Study Follow-Up Visits:

The study will consist of a 6-month visit post baseline (3-month post end of intervention). Participants will be asked to complete an in-person visit, if possible (telephone and online will be the alternative), which will include a second POCUS exam.

Subject Information

Target accrual: We plan to recruit 80 patients diagnosed with Post-Covid Syndrome at Mayo Clinic with the intent of enrolling 60 to study.

Subject population: A total of 60 patients diagnosed with Post-Covid Syndrome at Mayo Clinic who meet the following study criteria:

Inclusion Criteria:

- 1. 18 years of age or older at time of consent
- 2. Identified with Post-Covid Syndrome (PASC) at Mayo Clinic Rochester:

Wearable for LC

PIs: [name]; [name], PhD

Mayo Clinic - NCT05199233

- 3. Not pregnant by subject self-report at time of consent
- 4. Have the ability to provide informed consent
- 5. Have the ability to complete all aspects of this trial
- 6. Have access to an iPhone, iPad, or Android device
- 7. Have no contraindicating comorbid health condition which would interfere with the proper use of the Muse-STM system, as determined by the clinical investigators

Exclusion Criteria:

- 1. Used an investigational drug within the past 30 days
- 2. Anyone that is not on a stable dose of medication for anxiety, depression or sleep
- 3. Currently (within the past 3 weeks) been practicing mindfulness training on a weekly/regular basis
- 4. Currently (within 3 weeks) has been enrolled in another clinical or research program which intervenes on the patients' QOL, or stress
- 5. An unstable medical or mental health condition as determined by the physician investigator

Data Analysis

Data Analysis Plan:

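### Secondary hypothesis (a) is about change from baseline in as-directed users, but the only model for stress and sleep is specified to estimate a session-count association

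*Combined protocol and SAP*

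**What the plan says.** The combined protocol and SAP describes the target for stress and sleep in three places.

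- **Endpoints, secondary hypothesis (a):** stress will be lower and sleep better "when compared to the baseline measures for those who use the Muse-STM system as directed".
- **Data Analysis Plan:** "A linear mixed model with repeated measures for each time point that stress and sleep were taken" will be used to "estimate the association between the number of sessions spent using the Muse-STM with the stress and sleep level outcome". No visit term, baseline contrast, as-directed indicator or analysis set is named.
- **Secondary outcomes, listed after the aims:** change over time in stress is an outcome, with no restriction by adherence. Sleep is not on that list.

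There is no comparator: "All study participants will receive the Muse S^{TM} Headband system at study entry". The sample is 60, without a derivation. On status, the plan says "Given the number of outcomes assessed, all analyses will be considered exploratory", and "results will be summarized using point estimates and corresponding 95% confidence intervals".

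**The concern.** Whether someone used the device as directed is known only after the 12 treatment weeks, and stress and sleep are measured during those weeks (days 30, 60 and 90). People who feel better may keep meditating and people who worsen may stop. Membership of the group can then depend on the outcome, and a before-after change in that group can differ from the change in everyone enrolled. With no control arm, nothing in the data would expose this.

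The described model also targets something else. A slope of score on number of sessions is not a mean change from baseline, in adherers or in anyone. An analyst who follows the text would report an estimate that does not address hypothesis (a). An analyst who starts from the hypothesis would have to devise an unplanned analysis in a self-selected group.

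**Working it through.** The plan has no figure to reproduce: 60 is given without an effect size, SD, alpha or power. The check therefore compares the statements and then sizes the possible shift under assumptions.

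**1. The three statements side by side**

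| Place | Who | Quantity |
|---|---|---|
| Secondary outcomes list | all participants (no restriction stated) | change over time; stress but not sleep |
| Secondary hypothesis (a) | as-directed users | change from baseline; stress and sleep |
| Data Analysis Plan model | no subset stated | association of session count with score level; stress and sleep |

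No two rows agree on both group and quantity.

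**2. Shift from selecting on adherence**

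Shift in mean improvement = r × SD × φ(z)/p. Here p is the share as directed, z the normal cut-off leaving p above it, and r the correlation between adherence and improvement (bivariate normal). All inputs are assumptions: SD of PSS change 7, p from 0.3 to 0.7, r from -0.3 to 0.5. The PSS range of 0 to 40, higher being worse, is from Assessments.

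φ(z)/p is 0.348/0.3 = 1.159, 0.399/0.5 = 0.798 and 0.348/0.7 = 0.497. For example, at p = 0.5 and r = 0.3 the shift is 0.3 × 7 × 0.798 = 1.68. In PSS points, positive meaning in the device's favour:

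| p | r = -0.3 | r = 0 | r = 0.1 | r = 0.3 | r = 0.5 |
|---|---|---|---|---|---|
| 0.3 | -2.43 | 0 | 0.81 | 2.43 | 4.06 |
| 0.5 | -1.68 | 0 | 0.56 | 1.68 | 2.79 |
| 0.7 | -1.04 | 0 | 0.35 | 1.04 | 1.74 |

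With an SD of 5, the p = 0.5, r = 0.3 case is 0.3 × 5 × 0.798 = 1.20.

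**3. Compared with precision**

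The p = 0.5, r = 0.3 shift is 0.3 × 0.798 = 0.24 SD. The 95% CI half-width for a mean change is 1.96/√60 = 0.25 SD with all 60, and 1.96/√30 = 0.36 SD if only 30 were analysed (ratio √2 = 1.41).

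**4. Change and slope are different quantities**

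Simulation under assumed inputs: 60 people, days 0, 30, 60 and 90, no device effect, and a common trend of -3 PSS points by day 90. Session rates averaged 16 a month (SD 6), with 16 or more counted as directed, so about half qualify. Individual trend and visit-level error each had SD 3. The model had a random intercept and a running session count. Each row is the mean of 150 runs; ρ is the correlation of adherence with the underlying trend, positive when adherers improve more.

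| ρ | Change, all | Change, as directed | Slope per 48 sessions, visit in model | Slope, no visit |
|---|---|---|---|---|
| -0.3 | -2.96 | -2.29 | 2.39 | -2.24 |
| 0 | -3.06 | -3.01 | 0.05 | -2.63 |
| 0.3 | -3.03 | -3.72 | -2.21 | -2.92 |
| 0.5 | -2.95 | -4.15 | -3.98 | -3.09 |

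As a check, the formula predicts a shift of 0.3 × 3 × 0.798 = 0.72 at ρ = 0.3, and the simulation gave 3.72 - 3.03 = 0.69.

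At ρ = 0 everyone improves by about 3 points, yet the slope is near zero with visit in the model and -2.63 without it. The second value is only time, because a running count rises with each visit. The plan does not say how the count enters the model. At ρ = 0.3 the slope with visit is -2.21 although the device does nothing, so the session association carries the same selection.

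**5. The as-directed group has no analysis definition**

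The Methods text asks for four sessions a week over 12 weeks: 4 × 12 = 48. The Intervention text describes daily practice: 7 × 12 = 84. The minimum session lengths also differ (10 minutes in Methods, 5 for Mind Meditation).

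**The case against.** Four objections have force.

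- **Direction.** A reader might infer that the restriction necessarily flatters the device. The documents do not give the correlation between use and improvement. At zero there is no shift, and if people who recover stop using the device the shift reverses. Only a possible bias, probably favourable, can be claimed.
- **No adherers-only analysis is planned.** A reader might infer that non-adherers will be dropped and the interval widened by 41%. The restriction is in the wording of a hypothesis; the Data Analysis Plan defines no such subset. The shift and the loss of precision apply only if someone carries out that comparison.
- **The model could yield the change.** It uses every time point at which stress and sleep are taken, and the visit schedule includes day 0. With a visit term and a contrast it would give change from baseline. The fair statement is that it is not specified to do so, not that it cannot.
- **Stakes.** The primary outcome is adherence, summarised descriptively, and every analysis is labelled exploratory. For stress, the outcomes list already contains an unrestricted change over time.

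These points narrow the concern without removing it. An exploratory label does not supply a missing estimate, and for sleep not even the outcomes list gives an unrestricted change.

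**Conclusion.** The concern holds as a mismatch between hypothesis and model. Hypothesis (a) is about change from baseline in a group formed after baseline. The described model is specified to estimate a session-count association and states no visit effect or baseline-to-day-90 contrast. This rests on the text alone.

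The size of any bias is conditional. With an assumed SD of change of 7 PSS points and 50% as directed, a comparison in as-directed users shifts by 0 at correlation 0, by about 1.7 points in favour at 0.3 and by about 1.7 against at -0.3. A favourable shift is the more plausible, but the documents do not establish it.

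A reader might also infer that using all 60 participants would give the device effect. It would not: without a control arm, that change still includes natural recovery and regression to the mean. Because all analyses are exploratory, the severity is modest, but the plan should still be corrected.

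**What to change.** - Restate hypothesis (a) as change from baseline to day 90 in stress and sleep in all enrolled participants. Align the secondary outcomes list with it, adding sleep.
- Estimate that change from the mixed model with visit as a categorical fixed effect and baseline as the first repeated measure, and name the day-90 contrast.
- Keep the session-count association as a separate analysis with visit in the model. State how the count enters, and describe the result as an association.
- Reconcile the differing use instructions in the Methods and Intervention text, then define the as-directed group in advance. Report that group only as a descriptive subgroup, labelled as selected on post-baseline behaviour.
- State that, with no control arm, the change in all enrolled participants is not a device effect.

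The cost is analysis-plan wording. No new data, visits or participants are needed. The estimated change may turn out less favourable than one taken in as-directed users.
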